Risk differences (RDs) and risk ratios (RRs) will be estimated using cumulative incidences at day 75 after start of follow-up (i.e. day 14 after index date) for the 3. dose schedule being studied and the 2. dose comparator schedule, respectively in the matched populations. Comparative VE will be calculated as 1 – RR (for RR < 1.00). The propensity score for matching will be estimated as the probability of the 3. dose studied schedule conditional on covariates in the combined population of both schedules using logistic regression including direct adjustment for year of birth (5 year categories; proxy for age), sex, calendar month (monthly categories), comorbidity and vaccination priority group. We will calculate 95% CIs using the nonparametric bootstrap method with 1000 repetitions.

Meta-analyses

Where feasible, country-specific effect estimates will be combined using meta-analysis based on random-effects models implemented using *mixmeta* package of R. We will test for homogeneity of effects across countries using the Cochran Q test and will use the delta method to construct 95% CIs assuming independence. For those comparisons where metaanalysis are not feasible, we will present the country-specific results individually.

Intended additional analyses

In secondary analyses, we will stratify comparative VE estimates according to calendar periods of Alpha, Delta and Omicron variant dominance (i.e. when it is estimated that the variant of concern accounts for more than 90% of all cases) or using variant-PCR/WGS results, subject to national availability. These periods will be defined on a country-specific basis, based on the nationally surveillance data on variants of dominance.

Danish variant situation

The calendar periods for specific variant dominance in Denmark are: Alpha/Beta period, 15 March to 30 June 2021; Delta period: 15 July to 15 November 2021; and Omicron period: 28 December 2021 to 28 February 2022. The intermediary transition periods will be left out. As data availability permits, we will in addition assign each endpoint a variant using variantspecific test results or results from whole-genome sequencing (WGS). As an example, in Denmark we utilize both WGS and variant-PCR in covid-19 surveillance.

Finnish variant situation

Alpha/Beta period, 15 March to 9 May 2021; Delta period, 21 June to 27 November 2021; and Omicron period (BA.1), 1 January to 28 February 2022. The intermediary transition periods will be left out.

Norwegian variant situation

Alpha/Beta period, 8 March to 20 June, 2021; Delta period, 19 July to 19 December 2021; and Omicron period, 1 January to 28 February 2022. The intermediary transition periods will be left out.

Swedish variant situation

Alpha/Beta period, 8 March to 6 June 2021; Delta period, 10 July to 19 December 2021; and Omicron period, 3 January to 28 February 2022. The intermediary transition periods will be left out.

Waning

Differences in waning of immunity will be addressed in the head-to-head 2- vs. 2-dose and 3dose vs. 3-dose comparisons by estimating comparative VE using cumulative incidences at 30 day-intervals (i.e. day 120, 150, 180, 210, 240, 270, 300, 330, and 360 – to the extent that available data allows). Note that this will result in estimates of comparative waning, i.e. comparing cumulative incidences at day *X* for the heterologous studied schedule to cumulative incidences at day *X* for the homologous comparison schedule. Example: In the comparison of AZD1BNT2BNT3 vs BNT1BNT2BNT3 we observe a VE at day 75 against infection (testing positive) of 0% (i.e. no difference in cumulative incidences between the two schedules). At day 150, we observe a VE of 20%. Thus, we interpret this as the BNT1BNT2BNT3 waning more than the AZD1BNT1BNT3 schedule. Waning of immunity will also be evaluated within schedules, to the extent that the available data allows, by comparing cumulative incidences at day *X* to cumulative incidences at day 75.

Based on the data availability we will consider further subgrouping in relation to waning immunity such as by age groups.

Subgroup analysis according to age

We will conduct stratified analyses according to age groups of 18-40 years, 40-59, 60-74 and 75+, using birth cohort and age at index date – subject to the schedules and comparisons where we have data for this.

Children and adolescents population

As both the utilized vaccine schedules, time of vaccination, and doses differ among children and adolescents to the adult population, the vaccine effectiveness of children and adolescents will be examined in a separate cohort. Among adolescents (12- to 17-year olds), we intend to examine similar objectives as outlined for the adult population; however, these analyses will be confined to 2-dose regimens (as the countries have not yet consistently utilized a 3. [booster] dose for this younger population by the time of this study protocol). For children (5to 11-year olds), we will compare 1 or 2 doses to unvaccinated children (with a study design similar to that of the 3- vs. 2-dose comparisons in the main cohort), since only BNT162b2 has been used in this age group in the Nordic countries, precluding comparative measures. We will evaluate the following endpoints: infection, hospitalization and diagnosis of multisystem inflammatory syndrome in children (MIS-C).

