9.5 Study size (sample size and power)

We expect the Nordic countries to contribute with 19.6 million individuals vaccinated with at least two doses - based on a combined population of 23.1 million and a vaccination uptake of approximately 85% among individuals aged 12 years or older. The vaccination uptake in the 5to11-year olds will be lower: we expect at least 50% for one dose of vaccine in the countries that have recommended vaccination in this age group. The policy for vaccination 5- to 11-year olds was different in each country: Denmark recommended vaccination of all 5- to 11-year olds, Finland has also offered vaccination, while Norway and Sweden has recommended vaccination of risk groups among the 5- to 11-year olds. In all Nordic countries, the reduced dosage of BNT162b2 in two doses has been used in this age group. The statistical power will depend on the prevalence of the respective schedule being studied and the comparator schedule together with the frequency of the outcomes (PCR positive tests are not uncommon in individuals, while covid-19 hospitalization, ICU admission and deaths will be rarer). The Nordic countries have had similar mass vaccination rollouts with prioritized groups being vaccinated first followed by adult age groups; for both the primary series of 2-doses and for the 3rd booster dose. The two mRNA vaccines and the two viral vector vaccines have been in use in the Nordic countries; the BNT162b2 has been the most used type. The use of the

ChadOx1 viral vector vaccine early in the rollouts did differ between countries, with Denmark, Norway using it for frontline personnel, while Sweden, and Finland used it more generally. After the VITT signal the vaccine was discontinued first in Denmark and later followed by Norway. In Sweden and Finland, the use of the vaccine was initially restricted to 65 years or older after the VITT signal, but later the vaccine was discontinued. The restricted study designs that we will use may also reduce statistical power. However, this is a trade-off in the effort of constructing more comparable groups and, thus, better causal inference. The multi-country nature of our study will increase statistical power, especially for comparisons and outcomes where differences will be difficult to identify for single countries.

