9.7 Statistical analysis

Heterologous vs homologous comparisons – restriction to period- and age overlapping between groups

For the 2- vs 2- and 3- vs 3-dose comparisons (objective #1, heterologous vs homologous), the day the last vaccine was administered in the respective schedules will serve as the index date (see Figure 1 and 2). One main challenge is that vaccination schedules are correlated with age and calendar period. To certify that the vaccination periods (calendar periods where the specific schedule was used) and age intervals are similar between the comparative groups, we will identify the earliest and latest dates and youngest and oldest ages that comprises 95% of the vaccinated individuals in the heterologous schedule under study (i.e. studied schedule). These period- and age-intervals will serve as an eligibility criteria for the homologous comparison schedule vaccinated individuals. That is, to be included in the respective homologous vaccinated comparison schedule cohort, an individual will have to have received their index vaccine dose within the same period- and age-intervals as the heterologous vaccinated, that have received their index vaccine dose outside of the distinctly defined period- and age-95%-

intervals will be excluded from the cohort analysis. Adjustment will be accomplished through use of inverse probability weights – see subsection *Adjusted cumulative incidences* below. We will take the following potential confounders into account, age (5-year bins), calendar month of receiving the 2. or 3. dose (according to the compared schedules), sex, vaccination priority group and comorbidities.

[figure not shown]

[figure not shown]
3-dose vs 2-dose comparisons - restriction through matching

For the 3-dose vs 2-dose comparison (objective #2), we will use a 1-to-1 matched design, similar to previous work (See Figure 3 and 4).(17) The study period will be from the date when rollout of booster doses were initiated, specific for each country (e.g. 6 September 2021 for

Denmark and 17 September 2021 for Finland), and until 28 February 2022 (end of study period).

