At the day an individual receives a 3. dose (i.e. the index date) of the studied schedule, the individuals will be matched with an individual having received the respective 2-dose comparison schedule (i.e. controls) but have not yet received a 3. dose (i.e. at the this date). For each matched pair, the index date of the individual in the 3-dose studied schedule will be assigned to the 2-dose comparison schedule control individual. The matched controls will be eligible to be included in a 3-dose studied schedule group in case of receiving a future 3. dose to that of the given matched date. Individuals from the 3-dose studied and the 2-dose comparison schedules will be matched on age (5-year bins), calendar month of receiving the 2. dose and a propensity score summarizing potential confounders such as sex, vaccination priority group and comorbidity. The time at which an individual was vaccinated with a 2. dose, is highly correlated with risk of severe covid-19 and/or risk behavior due to the national prioritization of the rollout of the covid-19 vaccines (e.g. individuals of high risk of severe covid-19 and health care workers were prioritized for earlier vaccination than the general public).

Individuals in the country-specific cohorts will be followed from the time they enter one of the vaccination schedules groups and 13 days have passed until one of the endpoints included in the study, end of endpoint ascertainment period, received a booster dose (a 3. dose for 2-dose schedules and a 4. dose for 3-dose schedules), exit from the cohort due to death, loss to follow-up, emigration, or end of study period, whichever occurs first. I.e. for the 3- vs. 2-dose matched comparisons, follow-up for the matched pairs will also end if the control individual receives a 3. dose (on that date; see example in Figure 4B). Follow-up will be conducted separately for each outcome without censoring for the other study outcomes. That is, when evaluating effectiveness against covid-19 hospitalization to an ICU, having a positive PCR test for SARS-CoV-2 or being covid-19 hospitalized does not right-censor the follow-up for this individual. However, note that when the 14 days and 30 days, respectively, after a positive test has passed, the follow-up will be censored in the analyses of hospitalization and ICU, and mortality, respectively.

[figure not shown]

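### The propensity score for the 3-dose vs 2-dose matching is not tied to the matching date, so it is not guaranteed to balance sex, priority group and comorbidity at each date

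*Protocol*

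**What the plan says.** Section 9.7, under the matching heading for objective #2, builds 1-to-1 pairs in calendar order: "At the day an individual receives a 3. dose (i.e. the index date) of the studied schedule, the individuals will be matched" to a person with the comparison two-dose schedule "but have not yet received a 3. dose (i.e. at the this date"). The control takes over the case's index date. Crossing over is allowed: "The matched controls will be eligible to be included in a 3-dose studied schedule group in case of receiving a future 3. dose". Pairs are "matched on age (5-year bins), calendar month of receiving the 2. dose and a propensity score summarizing potential confounders such as sex, vaccination priority group". The score also carries comorbidity.

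The next part of section 9.7, on adjusted cumulative incidences for the same comparison, defines the score: "estimated as the probability of the 3. dose studied schedule conditional on covariates in the combined population of both schedules". It is a logistic regression on birth-year band, sex, calendar month, comorbidity and priority group. No matching date or set of people still eligible is mentioned.

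Section 9.5 describes the national rollouts as similar, "with prioritized groups being vaccinated first followed by adult age groups; for both the primary series of 2-doses and for the 3rd booster dose".

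Section 9.8 (two doses vs unvaccinated) says that it reuses the main design's matching variables, apart from dose-2 month, and lists age, sex, comorbidity and priority group.

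**The concern.** The score and the matching answer different questions. The matching needs people who were equally likely to be boosted on that date, given that both were still at two doses. The score, on its natural reading, gives the probability of belonging to one schedule rather than the other. A control who is boosted next month belongs to both schedules, so that person's outcome in the regression is either undefined or set by the future.

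Inside an age-by-dose-2-month cell, only the score is there to balance sex, priority group and comorbidity. If priority groups differ in when they were boosted more than in whether they were, their scores will be similar although their chances on a given day are not. A vulnerable person boosted early could then be paired with a non-vulnerable control. That would tilt the comparison for hospitalization, ICU admission and death.

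**Working it through.** The plan gives no figure to reproduce. The check has four steps.

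**1. When does a single score balance?** Within one age-by-dose-2-month cell, let h_t(x) be the probability of dose 3 in week t for a person with covariates x who is still at two doses. The probability of dose 3 by study end is e(x) = 1 − Π_t [1 − h_t(x)]. Balance at week t requires that people with equal score have equal h_t(x).
- If boosting hazards are proportional across groups, e(x) orders people as h_t(x) does, and the single score balances.
- If one group goes first and the other catches up, e(x) can be equal while h_t(x) differs. The score is then nearly flat, and a control picked within a caliper is close to a random draw from those not yet boosted.

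**2. Size of the imbalance.** From the protocol: 1-to-1 matching, the score covariates, and the Danish window of 6 September 2021 to 28 February 2022 (175 days, 25 weeks). Assumed: one cell of 6,000 people; target risk group 12%, health personnel 12%, relatives 2%, others 74%; sex; five comorbidity flags; pairing by nearest score or at random within 0.2 SD of the logit score. Shares are for the target risk group among pairs formed in weeks 1–8.

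| Timing of boosting | Score | Pairing | Boosted vs controls | SMD |
|---|---|---|---|---|
| Proportional, 82% boosted | single | nearest | 0.20 vs 0.20 | 0.00 |
| Proportional, 82% boosted | single | caliper | 0.20 vs 0.21 | −0.02 |
| Priority first, about 91% in all main groups | single | nearest | 0.37 vs 0.35 | +0.03 |
| Priority first, about 91% in all main groups | single | caliper | 0.37 vs 0.13 | +0.59 |
| Priority first | refitted each week | nearest | 0.37 vs 0.37 | +0.01 |
| Priority first | refitted each week | caliper | 0.37 vs 0.37 | 0.00 |

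Hand check of the fourth row: (0.37 − 0.13)/√[(0.37×0.63 + 0.13×0.87)/2] = 0.24/0.416 = 0.58; unrounded shares give 0.59. The control share of 0.13 is close to the cell's 0.12, as a near-random draw would give. In weeks 9–25 that scenario reverses: 0.04 vs 0.08, SMD −0.19.

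**3. From imbalance to risk.** If vulnerable people have four times the risk of others, with shares p1 among boosted and p0 among controls, the baseline-risk ratio is k = (1 + 3p1)/(1 + 3p0).
- Step 2, priority first, caliper, weeks 1–8: 2.11/1.39 = 1.52. Whole window: p1 = (1419×0.37 + 4005×0.04)/5424 = 0.126 and p0 = (1419×0.13 + 4005×0.08)/5424 = 0.093, so k = 1.378/1.279 = 1.08.
- Second set-up: 8% vulnerable, boosted in weeks 0–6, others in weeks 8–20, 90% coverage in all groups, caliper 0.1–0.2 SD. Shares of 11% vs 4.5–4.7% give 1.33/1.135 to 1.33/1.141, about 1.17. In weeks 0–7 alone the shares are 52–53% vs 19–21%, and k is about 1.6.
- Other equal-coverage runs with separated or overlapping timing: up to about 1.25 with a caliper; 1.08–1.10 with nearest score (1.06 in one run).
- Coverage 92/92/90% in vulnerable people, health personnel and others: runs disagree, from 1.01 to 1.22.
- Coverage 95/93/85%: 1.00–1.01.
- Direct matching on priority group: 1.00, with 0–5% fewer pairs.

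For a rare outcome, the observed risk ratio is about k times the true one, so comparative VE is understated by (k − 1)(1 − VE). At k = 1.25 that is a quarter of (1 − VE).

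**4. Where it would fall.** The Danish Delta period ends on 15 November 2021 and follow-up starts on day 14. Booster follow-up within Delta can therefore come only from index dates of 6 September to 1 November: 56 days, or 8 weeks. If the variant strata are cut by calendar time of follow-up, early imbalance would sit in the Delta stratum and could look like a difference between variants.

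**The case against.** Several points on the other side have force.

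- The protocol nowhere says that the score models ever being boosted. Section 9.3 defines calendar month by the index date, or by the dose examined, so the score might be read as partly date-specific. That reading cannot be carried out as written: a two-dose person has no index date before being matched. Using month of dose 2 for controls and of dose 3 for cases would largely separate the groups. What stands is that the text is ambiguous.
- Direct matching on age bin and dose-2 month removes much of the timing difference. Section 9.8 ties booster eligibility to time since dose 2, and section 9.5 describes the order of the whole rollout, not the order within such cells. This stands. It makes full separation of timing an extreme assumption, but overlapping timing with equal coverage and a caliper still gave 1.08–1.19 in one set of runs.
- Section 9.8 lists sex, comorbidity and priority group as matching variables of the main design, which is close to the remedy below. Section 9.7 nevertheless specifies a score, so the two sections need reconciling.
- Caliper and algorithm may be left to an analysis plan. True, but the score's model, outcome, population and covariates are already fixed here. Where nearest-score pairing works under equal coverage, it does so because chance differences in fitted score act as labels for covariate patterns.
- Safeguards exist: results by priority group (section 12) and a test-negative analysis adjusted for these covariates (section 9.8). The latter covers infection only. The former does not repair the overall estimate, and matched pairs need not share a priority group (about 9% did not in an equal-coverage caliper run).

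**Conclusion.** The point holds as a gap in what section 9.7 fixes. A score without a matching date is not guaranteed to balance sex, priority group and comorbidity among people who are matched day by day. Under the assumed inputs (vulnerable risk four times that of others) the baseline-risk ratio runs from about 1.00 when coverage differs clearly, through 1.08–1.10 with equal coverage and nearest-score matching, to about 1.25 with equal coverage and caliper matching. Group-specific uptake, timing within cells, caliper and pairing rule are not in the protocol, so the size cannot be fixed.

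A reader might infer more: that the score fails to balance early boosting, and that booster VE against severe outcomes is therefore understated by a known amount. The document does not support this. Proportional hazards or clearly different coverage leave almost no imbalance. The imbalance can reverse in later weeks and partly cancel. No figure was derived for infection, the primary outcome.

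**What to change.** In section 9.7, either:

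1. match directly on vaccination priority group, sex and a comorbidity summary (any/none, or a count of the five conditions), in addition to age bin and dose-2 month, which also agrees with the variables listed in section 9.8; or
2. estimate the score among people still at two doses and eligible at the matching date, for example weekly, and match on that date's score.

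In either case, state that calendar month in any score means month of dose 2, bring sections 9.7 and 9.8 into line, and report covariate balance by index period as well as overall.

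The cost is recoding one matching step with variables already defined in section 9.3. Some pairs will be lost, mainly vulnerable people with no remaining control: 0–5% across the runs with direct matching on priority group. Finer comorbidity cells would lose more.

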The endpoints will be: 1) a positive PCR test for SARS-CoV-2 (i.e. infection), 2) a covid-19 hospitalization, 3) covid-19 hospitalization at an intensive care unit (ICU) and 4) covid-19 related death. In the primary analyses we will follow up for the endpoints from start of follow-up defined as day 14 after the index date, and until 75 days have elapsed since the start of follow-up. These outcome ascertainment periods have been chosen to balance: a) that the follow-up among the comparison groups will be homogenous in contrast to longer periods of outcome ascertainment where right censoring at study end or another dose may differ substantially between comparison groups, and b) that we need to have sufficient follow-up for the assessment of hospitalization and mortality. When evaluating waning of immunity, follow-up for endpoints will continue beyond day 75.

Covid-19 hospitalization

Covid-19 hospitalization will be defined as an event fulfilling the following criteria: a) hospitalization with a PCR positive test for SARS-CoV-2 dated in the time period beginning 14 days before admission (day -14; the day of admission is day 0) and up to and including 2 days

after admission (day 2), b) inpatient hospital contact or a hospital contact with a duration of at least 12 hours and c) a covid-19 relevant diagnosis code (ICD-10: B342, B342A, B948A, B972, B972A, B972B, B972B1 or Z038PA1 – subject to country-specific coding practices, see table below - TIME-VARYING VARIABLES). Thus, individuals who are hospitalized for conditions not related to covid-19, but who coincidentally test positive in the period around admission (14 days before to 2 days after admission) will be included as an endpoint 1 (infection) but not an endpoint 2 (hospitalization). An example of this could be a patient with a fracture who test positive at admission as part of routine testing. This distinction is particularly important to make during periods of high incidence of infection as in the period of omicron. Covid-19 hospitalization to an ICU (endpoint 3) will be assessed among those individuals fulfilling the criteria for covid-19 hospitalization (endpoint 2).

Covid-19 related mortality

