Quality control analysis: 3- vs. 2-dose schedule comparisons using a test-negative case-control study design

As an additional quality control, we will apply a test-negative case-control study design as previously done(19,21) to estimate VE against infection (positive PCR test SARS-CoV-2) in 3-vs 2-dose schedule comparisons. The results of these analyses will be compared to the corresponding comparison results from our main analysis. This will inform us on the possible impact of selection bias arising from differences in who is being tested.

Data on all (positive or negative) test results for the period 27 December 2020 to 28 February 2022 will be extracted for those aged 18 years or older (as of 27 December 2020). We will exclude any negative PCR test results taken within 3 days of a previous negative test result (as these results likely represent the same episode), negative test results taken within 21 days before a positive test result (as these are likely to be false negative), and positive and negative test results within 90 days of a previous positive test result. Since we will be evaluating the effectiveness of a 3. dose, only PCR tests taken from the date where the booster doses rollout started, specific for each country (i.e. in Denmark: 6 September 2021 [week 37, 2021]), will be retained for analysis. Participants will contribute with only one randomly chosen negative test result in the follow-up period. The 3. (booster) doses will be identified after this date and there must be at least 6 months (from 6 September 2021 to 13 December 2021 - subject for country-specific variation) or 4.5 months (from 14 December 2021 to 28 February 2022) between the 2. and 3. dose or from 2. dose and onset (i.e. of covid-19 related event). These time periods of "since 2. dose" denotes whether an individuals is eligible of receiving a 3. dose as per national-specific health authority guidelines on booster vaccination rollout. The effectiveness of a 3. dose from day 14 to day 28 (after the index date) will be compared with 2. dose schedules with onsets of events after at least the abovementioned 6 or 4.5 months eligibility criterion as well as to the immediate short period after the booster dose (i.e. the first 2-6 days; day 0 and 1 will not be included due to the potential risk of bias related to any testing due to initial reactogenicity).

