9.9 Limitations of the research methods

Although, the planned comparative design mitigates potential bias in recording of healthcare information between vaccinated and unvaccinated, there are some potential limitations to the chosen methodological approach. First, our ascertainment of the study outcomes is dependent on secondary use of national microbiology test results. Depending on the country and period, we will not have complete registration of all infected in the population; only those tested positive. Second, we do not have information on symptoms for our PCR positive cases; thus, this outcome may contain both asymptomatic and symptomatic cases. Third, as noted in the 'Variables' subsection, our outcomes for severe covid-19 (hospitalization, ICU admission and covid-19 related death) may potentially capture individuals with an outcome not directly related to covid-19 but where covid-19 was a contributing factor or co-occurred. Fourth, while the study design has a high degree of generalizability to similar general populations, some clinical subgroups will not be studied, including: individuals who have received an Ad26.CoV2-S (Johnson & Johnson vaccine), as why the results will not directly help inform on the comparative VE for these situations. Similarly, the proposed study objectives do not include analysis on high-risk subgroups such as individuals with immunocompromised conditions. Fifth, our planned methodology, weighting (for the specified design to address objective #1) and matching (for the specified design to address objective #2) both have strengths and limitations. Advantages of weighting (as opposed to matching) is the potential of preserving a large majority of the total study sample and allowing the assessment of several treatment effects (i.e. average treatment effect for the whole population, ATE). A limitation to this approach is that in case of poor overlap of covariates distribution across comparative groups, this will lower statistical power. Matching has the advantages of providing a 1:1 comparison with intuitive estimates of average treatment effect in the treated (ATT), but limitations to this approach is the discarding of unmatched individuals, which reduces the sample size and generally does not allow for multiple comparisons. A final limitation is that many schedules are strongly correlated with calendar period. Since calendar period is also strongly correlated with variant dominance, the results of many of the schedule comparisons will be variant-specific.

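### A day-75 to day-150 change in comparative VE between booster schedules is read as waning, although the late follow-up comes from a shrinking, early-boosted group and, in Denmark and Finland, falls after Delta dominance

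*Protocol*

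**What the plan says.** Section 9.7 (Waning) compares cumulative incidences between schedules at 30-day steps from day 120 to day 360, as far as data allow, for both 2- vs 2-dose and 3- vs 3-dose comparisons. Its worked example is AZD1BNT2BNT3 against BNT1BNT2BNT3, with comparative VE against infection of 0% at day 75 and 20% at day 150. It ends: "Thus, we interpret this as the BNT1BNT2BNT3 waning more than the AZD1BNT1BNT3 schedule". (The last schedule name looks like a typing slip for AZD1BNT2BNT3.)

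The dates that govern this example are elsewhere:

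- Section 9.3 (Outcomes) sets "start of follow-up defined as day 14 after the index date, and until 75 days have elapsed since the start of follow-up".
- Section 9.8 gives the Danish booster start ("i.e. in Denmark: 6 September 2021 [week 37, 2021"). Section 9.7 repeats it and adds the Finnish start and the study end: "Denmark and 17 September 2021 for Finland), and until 28 February 2022 (end of study period". No start is given for Norway or Sweden.
- Section 9.7 lists variant periods, for Denmark "Delta period: 15 July to 15 November 2021; and Omicron period: 28 December 2021 to 28 February 2022". Delta dominance ends on 27 November 2021 in Finland and on 19 December 2021 in Norway and Sweden.
- Section 9.5 says that prioritised groups came first for the booster as well as for the primary series.

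Section 9.9 adds a general caution: "Since calendar period is also strongly correlated with variant dominance, the results of many of the schedule comparisons will be variant-specific".

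**The concern.** The example reads a change in a cumulative contrast as a property of time since dose. Two other things change along the same axis.

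First, follow-up ends on a fixed calendar date, so the later a person was boosted, the earlier that person leaves the curve. Cumulative incidence at day 150 is 1 − S(75) × S(150 | 75). S(75) is common to both time points, so the whole movement from day 75 to day 150 comes from S(150 | 75), which is estimated only from people boosted early enough to be there.

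Second, the early-boosted pass from Delta to Omicron as they pass from early to late follow-up.

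If schedules differ more in early-boosted priority groups than in later recipients, or differ against one variant and not the other, comparative VE can move with no waning in either arm. At stake is objective #4b: a report could state that one booster schedule wanes faster when the data do not identify that.

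**Working it through.** There is no plan figure to reproduce here, so the check is calendar arithmetic followed by an illustration.

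**Who can be observed at day X.** Latest index date = 28 Feb 2022 − (14 + X) days.

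| X | Days subtracted | Latest index date | Rollout days, Denmark (from 6 Sep) | Rollout days, Finland (from 17 Sep) |
|---|---|---|---|---|
| 75 | 89 | 1 Dec 2021 | 87 of 176 | – |
| 120 | 134 | 17 Oct 2021 | 42 | 31 |
| 150 | 164 | 17 Sep 2021 | 12 | 1 |
| 180 | 194 | 18 Aug 2021 | 0 | 0 |

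The results table shell in section 12 counts time from the index date. On that count day 150 needs a booster by 1 Oct 2021 (26 days in Denmark, 15 in Finland).

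**Which variant period follows day 75.** Earliest day 75 = booster start + 14 + 75.

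- Denmark: 6 Sep + 89 = 4 Dec 2021, 19 days after Delta dominance ended on 15 Nov.
- Finland: 17 Sep + 89 = 15 Dec 2021, 18 days after it ended on 27 Nov.
- Counted from the index date: 20 Nov and 1 Dec, still after Delta in both.
- Norway and Sweden: 19 Dec − 89 days = 21 Sep. Assumed starts of 1, 6, 17 and 21 Sep leave 20, 15, 4 and 0 Delta days after day 75.

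**Can the example's pattern arise with no waning?** I computed a deterministic Kaplan-Meier on the Danish dates. All inputs other than dates are assumptions: daily infection hazard in the comparator 0.0003 under Delta and 0.004 under Omicron, a linear transition between 15 Nov and 28 Dec, uniform uptake from 6 Sep to 28 Feb, and hazard ratios constant in time since dose, so no waning difference by construction.

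| Scenario | VE day 75 | VE day 150 |
|---|---|---|
| Composition: HR 0.5 if boosted by 17 Oct, 1.1 later | 2% | 20% |
| Composition: HR 0.6 and 1.1 | 0% | 15% |
| Composition: HR 0.7 and 1.1 | −2% | 10% |
| Variant only, cohort boosted 6–17 Sep: HR 1.0 Delta, 0.75 Omicron | 14.5% | 20.5% |
| Variant only, all index dates pooled, same HRs | 22% | 20% |
| No difference anywhere | 0% | 0% |

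The composition rows reproduce the size of the protocol's example. The variant mechanism produces a rise in a fixed early cohort but not in the pooled curve, because most people in the pooled curve already meet Omicron before day 75.

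**The case against.** The disputed sentence is a worked example for an exploratory objective. Section 8 says that objectives #3 to #5 are evaluated only where information suffices and that 3-dose waning is limited by study end. Section 9.7 restricts the time points to what the data allow, which already deals with day 180 and later. Section 9.9 warns that many comparisons will be variant-specific, variant-stratified VE is planned, and the weights include calendar month of the index dose.

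Much of this is fair, and it limits how serious the point is. It does not repair the interpretation. The availability proviso governs which time points appear, not what they mean. The section 9.9 caution is not tied to waning. Section 12 lists waning and variant as separate breakdowns, not crossed. Index-month weighting makes the arms alike at baseline; it does not make those left at day 150 resemble those at day 75.

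A reader might infer more than the protocol supports:

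- **That all booster follow-up past day 75 is post-Delta.** This holds for Denmark and Finland only.
- **That everything past day 75 comes from the earliest-boosted.** This fits days 120 to 150. Just past day 75, anyone boosted up to 1 December contributes.
- **That a variant-specific effect alone turns 0% into 20%.** Not in the pooled estimator. With VE 0% against Delta and 40% against Omicron, uniform uptake, and daily Delta/Omicron hazards of 0.0003/0.004, 0.0005/0.002 and 0.001/0.001, comparative VE is already 27–36% at day 75 and is 32–35% at day 150.
- **That objective #4b as a whole collapses into objective #3.** The dates above say nothing about the 2- vs 2-dose waning comparisons.

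**Conclusion.** The point stands for 3- vs 3-dose waning. The protocol's reading of a day-75 to day-150 change as one schedule waning more is not identified. The group at risk shrinks from index dates up to 1 December 2021 at day 75 to 12 Danish rollout days and one Finnish day at day 150, drawn from a rollout that served priority groups first. A movement of the size in the example (about 2% to 20%) can arise with no waning, mainly through this change in who is observed and, within a fixed early cohort, also through a variant-specific difference.

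The dates assume that the rollout starts given for objective #2 also bound the 3- vs 3-dose comparisons. A third dose given earlier, more than 90 days after the second, is not excluded, so a few earlier index dates are possible. The size of the illustration rests on assumed hazards, hazard ratios and uptake. It shows that the pattern is possible, not that it is likely, and a true null in every group stays at 0%.

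**What to change.** For 3- vs 3-dose waning:

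1. Compute the day-75 and day-X values in the same index-date cohort, namely people boosted early enough to reach day X by 28 February 2022.
2. Report comparative VE by interval as well as cumulatively, with numbers at risk at each time point.
3. Where data allow, repeat within one variant period and within index-month strata, re-estimating the weights among those who enter. Time-since-dose bands within the Omicron period are not enough alone: in so short a window they still set early-boosted people against later-boosted ones, and weights estimated at the index date need not balance those who enter later.
4. Replace the interpretive sentence with wording such as: change with time since dose and/or variant. Call it comparative waning only if it persists within the same cohort and variant period. Correct the schedule name in that sentence at the same time.

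This uses existing data and means reprogramming one secondary analysis. The price is wider intervals and few or no estimable time points at day 150 and later.
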